Once project staff receive the completed surveys and consent forms, participating families will be randomly assigned to one of three conditions (web/mobile- only, web/mobile + coach, or waitlist control). Participants will then receive an email that provides instructions about next steps. This email will vary based on condition. Participants in the **web/mobile-only condition** will receive an email with an explanation about the website and information about how to log in. Participants in the **web/mobile + coach condition** will receive an email with an explanation of the website, information about how to log in, and the name and email address of the coach who will be working with them. The coach will contact families in this second condition after they log in to the website for the first time, unless the participant reaches out to the coach first. Participants in the **waitlist control group** will receive an email thanking them for their participation and letting them know that they will next be contacted by project staff in 3 months.

Participants in the **web-mobile only** condition will log on to the FCU Online website where they will complete an intervention assessment, receive feedback on their data, and be provided with online tools to support their parenting in areas that were identified as challenges by the assessment (see fuller description below in section 3). These tools include videos, animated videos, parenting tips, and interactives. Parents will also be given the opportunity to practice parenting skills and track their progress. Parents who choose to engage in this practice will have the opportunity to receive text messaging that prompts them to try out new skills learned from the website. Parents will be able to log-in as often as they like and interact with any of the parenting Skills Sessions on the website.

Participants in the **web-mobile + coach condition** will log on to the same FCU Online website where they will have access to the same assessment, materials, and tools. In addition, a Family Coach will contact them to help them set goals, talk through their results, offer support over the phone, and help motivate parents to improve parenting practices. Parents will be able to log-in as often as they like and interact with any of the parenting Skills Sessions on the website. They will also be able to contact their Family Coach as often as they like and will have at least 2 scheduled phone sessions with a coach.

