Families in all three conditions will be invited to participate in follow-up questionnaires at 3 months, 6 months, and 12 months that will be identical to the pre-assessment so that we can evaluate change over time in the assessed constructs. The estimated time needed for parents and youth to complete each of these follow-up questionnaires is 30 minutes. At each of these three assessment points parents and youth will be mailed a questionnaire packet and return them independently to the research team in their own self-addressed stamped envelope. At the time of the 3-month follow up, parents in the two intervention conditions will also complete a 2-page Website Feedback Survey. These surveys will also be completed by mail.

All families will be compensated for their time. Each family will receive \$100 for completing assessments at baseline, 3 months, 6 months, and 12 months for a total of \$400. Because sustained family involvement in a longitudinal study is critical to maintain, families will be offered a \$50 bonus if they complete all 4 assessment points.

Unfortunately, the website is only offered in English. However, Spanish-speaking families at these schools will still be offered options to allow them to participate in the study and/ or receive the intervention if they desire. Spanish speakers who are comfortable reading English will be randomly assigned to one of the three experimental conditions described above, but will have an option to complete the pre-assessment and follow-up assessments in either English or Spanish (and the website in English). Those who are not comfortable reading English will still be offered the opportunity to participate and be compensated, but will be assigned to a **nonexperimental tele-health condition** described below. All of the information available online in the parenting skills modules has been translated into Spanish and will be presented to these families via pamphlets.

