Because the focus of the implementation study is school staff rather than parents, we will not be collecting baseline surveys or any of the follow-up surveys used in the main research study. Rather, parents will be identified by coaches, and enrolled directly in the website. After providing informed consent, parents will complete a qualtrics form that includes the information needed to enroll them in the website. The data provided via this form will be sent directly to research staff, who will use it to enter participants into the administrative website that triggers an email to participants thanking them for their willingness to participate and includes log-in information and directions for how to get started. Parents will complete the survey that is built into the website, receive computer generated feedback, and will then meet with their coach to discuss the feedback and the parenting modules presented on the website. The survey takes about 30 minutes to complete; parents may log-in and use the parenting resources as little or as often as they would like.

At the end of the study, parents will be asked to complete a 2-page Website Satisfaction Survey which will take about 10 minutes to complete. This survey will be administered via Qualtrics. An email with a link to the survey will be sent to parents approximately 6 months after they are enrolled in the study.

At the end of the study, coaches will be interviewed one-on-one by a member of the research team about the ways that they were able to use the website to work with families, any challenges that they encountered, and their insights into factors that could be improved to enhance implementation in schools. This interview will take approximately 1 hour.

Analysis

For our preliminary analyses, we will compare baseline characteristics of participants across conditions to test for significant differences; characteristics that differ across conditions will be used as covariates in subsequent analyses. Logistic regression analyses will be used to examine potential differences by study condition between dropouts and continuing participants on baseline measures. Attrition analyses will provide information about the external validity of the study, and interaction effects between condition and predictors will provide information about potential confounding effects (Cook & Campbell, 1979).

Aim 1: Design and evaluate a web-based FCU intervention that is guided by feedback from focus groups.

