Aim 2.1: Analysis of main effects. The hypotheses tested in this aim are (a) families in each intervention condition will show significant improvements on the outcome variables, compared with youths in the control condition, and (b) families assigned to the web/mobile+ coach condition will have significantly better outcomes compared with those assigned to the web/mobile-only condition. The primary outcomes include academic competence, youth behavioral control, delayed onset of youth substance use, reduced family conflict, increased family cohesion, and positive family relationships. The secondary outcomes include the putative mediating mechanisms of parenting skills and behaviors. Families will be randomized to condition and will be the unit of analysis for all models. Mixed-effects analyses will be based on a hierarchical linear modeling approach in which students are nested within schools, primary outcomes are nested within individual students at Level 1 of the model, and between-subject predictors (fixed effects), such as treatment condition and child/parent demographics, will be examined at Level 2. For each of the three pairwise contrasts between conditions, intervention effects will be examined by modeling longitudinal trajectories across time with mixed-effects models using SAS PROC MIXED or mPlus software.

Aim 2.2: Mediation model testing. We will test whether change in the putative mediating mechanisms of parenting skills and behaviors (e.g., change from baseline to 3-month follow-up) mediate the association between study conditions and longitudinal trajectories of the youth and family outcomes.

Aim 2.3: Examine moderating effects and intervention process measures. The moderation analyses will follow recommendations by Kraemer and colleagues (2002) and analytic methods of Aiken and West (1991), Jaccard and Turrisi (2003), and Preacher et al. (2006). Because we do not have specific hypotheses

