Official Title: Prevention of Substance Use in At-Risk Students: A Family-Centered Web Program

NCT Number: NCT03060291

Document Date: July 14, 2020

Statistical Analysis Plan with Results Information

Data Analysis

Preliminary analyses included descriptive statistics and plots to screen outcomes for normality. Chi-square statistics and one-way ANOVA models were used to compare study condition and demographic characteristics between participants who dropped out of the study versus those who completed all four assessments.

Intent-to-treat analyses of condition effects were evaluated with mixed effects growth models using SAS 9.2 PROC MIXED and estimated using full-information maximum likelihood, an unstructured variance and covariance matrix, and random intercepts and slopes. Variability in outcomes from pretest to 1-year follow-up was modeled as a function of condition, time (coded in months), and a condition \times time interaction term. The intercept was specified at the 1-year follow-up assessment; thus, the condition effect is a test of whether intervention groups differed at the end of the study. Following Singer and Willet (2003), when constructing the longitudinal model we (a) examined empirical growth plots; (b) fit an unconditional means model; (c) fit an unconditional linear growth model; (d) fit unconditional non-linear models; and (e) compared models of longitudinal change using the Akaike Information Criterion. Three a priori dummy coded comparisons were examined: wait-list control (reference group) versus web-only, wait-list control (reference group) versus web plus coach, and web-only (reference group) versus web plus coach. Effect sizes for the condition effect at the end of the study are reported as Cohen's d (Cohen, 1988) and computed as model estimated differences in the outcomes at 1-year follow-up divided by the observed baseline pooled standard deviation.

Results

Preliminary analyses. Demographic make-up of the sample, program use metrics, baseline equivalency of the three intervention groups, and correlations of the pretest measures

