have been previously reported (Stormshak et. al., 2019). Briefly, parents in the study were predominately female, on average 40.0 ($SD = 6.1$) years of age, and 35% had a 4-year college degree or graduate training. The children in the study were approximately gender balanced, mostly white, and mostly lived in suburban environments. Use of the site was robust, but the web plus coach group used the program significantly more than the web-only group. Participants in the three conditions did not differ on gender, area (rural, suburban, urban), minority status, SES risk score or pretest measures of the outcomes indicating randomization produced initially equivalent groups. The correlations of the pretest measures ranged from $r = -.67$ to $r = .60$ (mean $|r| = .30$).

The outcomes approximated normal distributions except conduct problems which was normalized with a logarithmic transformation. Complete data was available for 88% of the sample and attrition was 6% at posttest, 8% at 6-month follow-up and 9% at 1-year follow-up. Number of assessments completed was not significantly associated with study condition, child's gender and child's race (all p -values $> .08$). Comparison of linear and non-linear unconditional models showed a linear model had superior fit to a linear and quadtric model for all study outcomes.

Table 1 provides means and standard deviations for the outcomes at each assessment point for each of the three conditions. Table 2 provides a summary of the condition effects from the growth models for the three a priori comparisons and is a test of whether groups differed in change in outcomes from pretest to the 1-year follow-up. No statistically significant (at $p < .017$) differences were found, although one trend-level effect ($p < .10$) is worth noting. The web plus coach group showed trend level differences in sense of parenting importance that favored the

web plus coach group relative to the wait-list control group, a small to medium effect (p -value = .081, $d = .28$), a small to medium effect (Cohen, 1988).

	Pretest		3-Month Posttest		6-Month Follow-up		1-Year Follow-up	
	M	SD	M	SD	M	SD	M	SD
Wait-list control	1.05	1.38	1.24	1.54	1.00	1.44	1.08	1.45
Web-only intervention	1.37	1.81	1.32	1.63	1.17	1.57	1.19	1.40
Web plus coach intervention	1.44	1.65	1.30	1.55	1.12	1.54	1.21	1.60
Hyperactivity								
Wait-list control	3.45	2.69	3.31	3.43	3.24	2.32	3.46	2.56

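### The growth model gives each arm its own pretest mean, so the 12-month contrasts are not conditioned on a pretest collected before randomisation; the precision forgone depends on a pretest-to-12-month correlation that is not reported

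*SAP*

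**What the plan says.** **The model.** SAP, Data Analysis: "Variability in outcomes from pretest to 1-year follow-up was modeled as a function of condition, time (coded in months), and a condition"-by-time interaction. The intercept is placed at 1 year, so that "the condition effect is a test of whether intervention groups differed at the end of the study". No pretest covariate and no common-baseline constraint is described.

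**The description of its results.** SAP, Results, says of the condition effects in Table 2 that the table "is a test of whether groups differed in change in outcomes from pretest to the 1-year follow-up".

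**Covariates.** Protocol section C, Analysis (preliminary analyses): "characteristics that differ across conditions will be used as covariates in subsequent analyses". Under Aim 2.1 the between-subject predictors are those "such as treatment condition and child/parent demographics, will be examined at Level 2". Under Aim 2.3, baseline severity of child behaviour appears as a possible moderator, in analyses labelled exploratory. The SAP then lists what did not differ between arms, ending with "SES risk score or pretest measures of the outcomes indicating randomization produced initially equivalent groups".

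**Timing.** Protocol section C, Main Research Study: "Once project staff receive the completed surveys and consent forms, participating families will be randomly assigned to one of three conditions". The follow-up questionnaires "will be identical to the pre-assessment so that we can evaluate change over time in the assessed constructs".

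**The concern.** The pretest is returned before assignment and uses the same instrument as follow-up. A pretest gap between randomised arms is therefore chance, and assuming one common pretest mean is valid by design. The model does not use this. With a free condition effect and a free condition-by-time effect, each arm's line has its own intercept and slope, and so its own pretest mean.

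The protocol's covariate rule does not fill the gap. It depends on whether arms differ at baseline, whereas the value of adjusting for pretest depends on how well pretest predicts the outcome. A gap that passes the screen stays in the data.

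All 21 contrasts are reported as non-significant at .017, so unused precision matters to a reader. In addition, anyone relying on the Results description of Table 2 would think that pretest differences had been removed.

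**Working it through.** **1. Gaps left by the screen.** Table 1 pretest values, coach versus wait-list:
- Hyperactivity: 4.19 − 3.45 = 0.74; pooled SD √[(2.69² + 2.87²)/2] = 2.78; gap 0.27 SD.
- Emotional problems: 2.78 − 2.34 = 0.44; pooled SD √[(2.27² + 2.12²)/2] = 2.20; gap 0.20 SD.

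The protocol gives no alpha for the screen. Assuming .05 and the planned 100 per arm, a pairwise gap must reach 1.972 × √(2/100) = 0.28 SD. A three-arm F test on the same inputs gives p = .14 (hyperactivity) and p = .38 (emotional problems). Both outcomes pass and stay unadjusted.

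**2. Standard error of the 12-month contrast.** Visits are at t = 0, 3, 6 and 12 months. Assume equal variances, complete data and correlation matrix R. For the between-arm difference, the variance is the relevant element of (X′R⁻¹X)⁻¹:
- Current model: X = [1, t − 12], first element.
- Option A, common pretest mean: X = [t/12].
- Option B, pretest as covariate: difference fixed at 0 at t = 0, with a free line over 3, 6 and 12 months read at 12.

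The documents give no pre-post correlation. The −.67 to .60 in the SAP is between different pretest measures. Two patterns are assumed: equal correlation at all lags, and first-order autoregressive decay, AR(1). Standard errors are in units where a raw single-visit contrast has SE 1.

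| Pattern | Pretest-to-12-month r | Current | A | Change, A | B | Change, B |
|---|---|---|---|---|---|---|
| Equal | .3 | .938 | .919 | −2.0% | .927 | −1.1% |
| AR(1) | .3 | .990 | .949 | −4.1% | .951 | −3.9% |
| Equal | .5 | .956 | .845 | −11.6% | .845 | −11.6% |
| AR(1) | .5 | .997 | .865 | −13.2% | .866 | −13.2% |
| Equal | .7 | .974 | .695 | −28.6% | .699 | −28.2% |
| AR(1) | .7 | .999 | .714 | −28.6% | .714 | −28.5% |
| AR(1), 3-month r = .5 | .06 | .959 | .959 | 0.0% | .981 | +2.3% |
| AR(1), 3-month r = .3 | .01 | .931 | .918 | −1.4% | .968 | +4.0% |

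Once the pretest-to-12-month correlation is fixed, the choice between these two patterns matters little. Under equal correlation the cut from A is worth (.938/.919)² − 1 = 4%, (.956/.845)² − 1 = 28% or (.974/.695)² − 1 = 96% more families.

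**3. Share of a pretest gap kept.** Under equal correlation the current contrast weights the four visits −.20, .057, .314 and .829. Given a pretest gap, the expected share carried into the 12-month contrast is −.20 + 1.20r, or .16, .40 and .64 at r = .3, .5 and .7. For emotional problems (gap 0.44) that is 0.07, 0.18 or 0.28 points, against a reported SE of .30. For hyperactivity (gap 0.74) it is 0.12, 0.30 or 0.47, against .34. With AR(1) and 3-month r = .5 the share is about −.02, that is, almost nothing.

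**4. What Table 2 estimates.** Reported estimate, raw 12-month difference and difference in change from pretest, for the two outcomes with labelled rows in the Table 1 text available:

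| Outcome, contrast | Reported | 12-month | Change |
|---|---|---|---|
| Hyperactivity, wait-list vs web | −0.17 | −0.25 | −0.52 |
| Hyperactivity, wait-list vs coach | 0.22 | −0.05 | −0.79 |
| Hyperactivity, web vs coach | 0.36 | 0.20 | −0.27 |
| Emotional, wait-list vs web | 0.06 | 0.04 | −0.18 |
| Emotional, wait-list vs coach | −0.47 | −0.51 | −0.95 |
| Emotional, web vs coach | −0.51 | −0.55 | −0.77 |

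All six lie closer to the 12-month difference, which agrees with the definition in Data Analysis and not with the Results sentence.

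**The case against.** A linear growth model with free arm intercepts is a recognised analysis and is unbiased over randomisation. A reader might infer that the missing adjustment biases the trial or that randomisation failed. Neither follows: gaps of 0.20 to 0.27 SD are compatible with chance at this size.

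A reader might also take the 29% as this trial's loss. The documents do not support that, because the correlation is unknown. The published standard errors do not settle it either. With an assumed 91 per arm (100 less 9% attrition), the six checkable ones are 0.91 to 0.95 of the raw 12-month standard error. That fits an unadjusted model but does not identify r.

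The carry-over figures are expectations given a gap, not predictions of a refit. The linear fit to Table 1 means misses Table 2 in all six contrasts, by as much as 0.33 for hyperactivity, coach versus wait-list.

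The Aim 2.1 predictor list is illustrative, and Aim 2.3 does plan to model baseline severity, but only as an exploratory moderator. The SAP's main model contains no such term. Each remedy also has a cost, set out below.

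These points limit the size and the tone. They do not remove the omission, or the conflict between the two descriptions of Table 2.

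**Conclusion.** The concern stands as one of precision and chance imbalance. The 12-month contrast is not conditioned on a pretest measured before randomisation, and the baseline screen leaves it so. A common pretest mean would reduce the standard error by about 2–4% if the pretest-to-12-month correlation is .3, 12–13% if .5, 29% if .7, and 0–1% if near zero. These figures assume linear change, equal variances, complete data and the two correlation patterns shown.

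It is tempting to conclude that some of the 21 null results would become significant. The documents do not show this: the correlation is missing and Table 1 means do not reproduce Table 2.

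The two SAP descriptions of the Table 2 parameter conflict. The end-of-study definition is the one that the checkable estimates support.

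**What to change.** Replace the baseline-significance screen with pretest adjustment for every outcome, whatever the baseline p-values. Either option will do:
- **A.** Keep the same PROC MIXED model, code time 0, 3, 6 and 12, drop the condition main effect, and report 12 × the condition-by-time coefficient.
- **B.** Model the 3-, 6- and 12-month outcomes with pretest and pretest-by-time as covariates, plus condition and condition-by-time centred at month 12.

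State the downsides. A assumes that the effect grows linearly from zero, which Table 1 does not clearly show: coach minus wait-list change at 3, 6 and 12 months is −0.80, −0.60, −0.95 (emotional problems) and −0.58, −0.53, −0.79 (hyperactivity). B avoids that assumption but loses about 2–4% precision if the 12-month correlation is near zero.

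Report all 21 refitted contrasts beside the originals as a labelled post hoc sensitivity analysis, with each outcome's pre-post correlation. Change the Results sentence on Table 2 to say that it tests the difference at 1 year.

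The cost is a few lines of code and wording, on data already collected. Two further matters do not depend on this point and should be checked separately: the +0.22 for hyperactivity, coach versus wait-list, against a raw difference of −0.05; and Table 2 contrasts that do not add up within rounding (hyperactivity: 0.22 − (−0.17) = 0.39, reported 0.36; emotional problems: −0.47 − 0.06 = −0.53, reported −0.51).

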We will recruit and randomly assign 300 families with middle school youths (6th and 7th grade) to one of three conditions: (a) web/mobile + coach intervention (n=100), (b) web/ mobile-only intervention (n=100), or (c) waitlist control group (n=100) that will receive middle school as usual and then offered the web/mobile-only intervention immediately after completing their final time point of data collection (12 months after enrollment). This design will enable us to compare outcomes associated with the web/ mobile-only intervention with a coach version. Participants will be randomly assigned to condition within school such that each school will have a similar number of participants in each of the three conditions. Participation in this study will be 12 months for all families, regardless of condition.

Families in all three conditions will be mailed a packet that includes a parent consent form, youth assent form, the parent and youth surveys, and 4 self-addressed, stamped envelopes so that each consent and survey may be mailed back separately to project staff. This “pre-assessment” includes standard, widely-used questionnaires that ask questions about the child's abilities and behavior, parenting practices, family dynamics, family demographics, family health behaviors, and life stressors and take about 30 minutes to complete. At the time of the pre-assessment, parents will also be asked to provide research staff with their driver's license number. We collect these because they assist us in relocating families for subsequent phases

of this longitudinal research project if they were to become lost. Our research team subscribes to a service which allows us to search for individuals by DL numbers to obtain a new address or phone number from items such as utility bills. Driver's license numbers will be retained for the duration of the research project. Participants will be assured that this information will be kept private, consistent with other data collected, and will be destroyed no later than 5 years after the end of the project.

One week after mailing this packet, a paid staff member will call the caregiver to see if the caregiver or youth have any questions about the consent form or the survey. If the family has not yet returned their surveys, they will be reminded to do so as soon as possible.

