If a parent meets inclusion criteria, the staff member will proceed in explaining the goals of the Pilot Study and providing details about participation. Parents who still indicate interest in the study after hearing these details will then be sent a packet that includes a parent consent form, youth assent form, the parent and youth surveys, and 4 self-addressed, stamped envelopes so that each consent and survey may be mailed back separately to project staff. One week after mailing this packet, a paid staff member will call the caregiver, go over the Pilot Study consent form over the phone, and see if the caregiver has any questions about the consent form or the survey. If the caregiver has not yet returned the surveys, he/ she will be reminded to do so as soon as possible.

Pilot Study families will be paid \$200 for their participation, paid in two chunks of \$100 each. Families will receive one \$100 check per household after completing the baseline pre-assessment; they will receive a second \$100 check after completing the post-test and attending a short meeting with a staff member to provide feedback on their research experience. As additional compensation, pilot study participants will have unlimited access to the full website after it is finalized for the main study and may utilize the tips and tools as often as desired.

Main Project Participant population and research setting:

All families of 6th and 7th grade students enrolled at one of 6 middle schools during the 2016-2017 or 2017-2018 school year will be recruited to participate in the main research study. Our target sample is 300 middle school students and their parents. The ethnicity of the sample is expected to be consistent with that of families in Oregon, with about 78% white, 12% Latino, 5% Asian American, and 5% African American. Because our target sample size is 300 students, we plan to accept approximately 50 families from each of the 6 schools. Recruitment will occur over two years, with approximately 100 intervention and 50 control families recruited for the study each year.

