The sample will be recruited from 6 economically disadvantaged middle schools in Oregon, 2 each in urban, suburban, and rural areas of the state. We selected schools based on the percentage of students who qualify for free and reduced lunch. The percentage of qualifying students at each school is higher than the state average of 55%. We chose to recruit families from these three settings to increase the generalizability of our findings. Youths in these three settings may have different community norms regarding problem behaviors, and differential access to public transportation may mean different manners of engaging in problem behavior (i.e., different degrees of access to drugs, alcohol, and deviant peers). Families in these three settings may have different community norms regarding parenting behavior, and different degrees of access to mental health services or support for positive parenting. They may also utilize web-based resources with different frequency. Thus, it is important to see whether there are community effects on the successful uptake of a web-based parenting intervention.

Recruitment Process:

The principal at each school will send out an email to parents of 6th and 7th graders advertising this research opportunity (“Principal Recruitment Email” and “Spanish Principal Recruitment Email”). This email will explain the study, and include a link to a Qualtrics contact form where interested parents could list their contact information. A paid staff member would then contact all the parents who provided contact information in order to explain the goals of the study and provide details about participation. Parents who indicate interest in the study and meet inclusion criteria will then be mailed a packet that includes a parent consent form, youth assent form, and the parent and youth surveys. Spanish speakers will be asked whether they are more comfortable reading information in English, Spanish, or either. Those who indicate Spanish as the preferred language will be assigned to the nonexperimental tele-health treatment group and will receive all materials and contact with project staff in Spanish. Those who indicate that they are comfortable reading in either language will be given a choice of English or Spanish surveys and then randomly assigned to one of the three experimental conditions.

The following criteria exist for inclusion/ exclusion in this research study:

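### The SAP growth model describes no school term although families were to be randomised within six schools; if it was fitted as described, standard errors are probably about 1% to 5% too large.

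*SAP*

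**What the plan says.** **Randomisation.** Protocol section C.3 (Main Research Study): "Participants will be randomly assigned to condition within school such that each school will have a similar number of participants in each" condition. Section D gives the planned sizes: "we plan to accept approximately 50 families from each of the 6 schools".

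**Protocol analysis.** Aim 2.1: "Mixed-effects analyses will be based on a hierarchical linear modeling approach in which students are nested within schools". The sentence then continues "primary outcomes are nested within individual students at Level 1 of the model" and puts between-subject predictors at Level 2. No level or term is assigned to school. The same paragraph makes the family both the unit of randomisation and the unit of analysis.

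**SAP analysis.** Under Data Analysis, outcome variability "was modeled as a function of condition, time (coded in months), and a condition" by time interaction. Estimation uses "an unstructured variance and covariance matrix, and random intercepts and slopes"; the unit over which the intercepts and slopes vary is not named. The intercept is placed at one year, so the condition coefficient is the end-of-study contrast. School does not appear.

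**Related text.** Section D of the protocol expects settings to differ: "Youths in these three settings may have different community norms regarding problem behaviors". The SAP results summarise balance by area: "Participants in the three conditions did not differ on gender, area (rural, suburban, urban". They give no counts by school.

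**The concern.** School is the planned randomisation stratum, and the protocol names it as a level of the data. An analysis that leaves it out does not match the randomisation, and the SAP gives no reason for doing so.

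When arms are balanced within each school, school differences cancel out of an arm contrast. If the model has no school term, those differences remain in its residual variance. The reported standard error is then larger than the true one. What is at stake is some precision, and a reader's ability to tell whether the planned nesting was used.

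**Working it through.** **Plan's own figures.** Three contrasts per outcome give .05/3 = .0167, which rounds to the SAP's .017. The smallest p-value in Table 2 is .081 (t = 1.75, sense of parenting importance, wait-list versus web plus coach). A t of 1.75 gives a two-sided p of .0817 on 200 df and .0812 on 297 df, so it reproduces within rounding.

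**Inputs.** From the protocol: 6 schools and n = 100 per arm, so 100/6 = 16.67 per arm per school. Assumed: ICC of .02, .05 or .10, equal schools, exact balance within school, a common effect, and total variance 1.

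**Formula (end-of-study contrast, one wave).**
- True variance of an arm difference: (2/n)(1 − ICC), because the school effects cancel.
- Variance that a model without school reports: (2/n)[(1 − ICC) + ICC(n − n/6)/(n − 1)], with (100 − 16.67)/99 = 0.8418.
- Ratio R of reported to true standard error: the square root of the second divided by the first.
- True error at nominal .017: 2[1 − Φ(2.387R)].
- Power without school, where the adjusted power is 80%: 1 − Φ(2.387R − (2.387 + 0.842)).

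Example at ICC .05: .95 + .05 × .8418 = .9921, and R = √(.9921/.95) = 1.022.

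| Assumed ICC | R | True error at .017 | Power (80% if adjusted) |
|---|---|---|---|
| .02 | 1.009 | .0161 | 79.4% |
| .05 | 1.022 | .0147 | 78.5% |
| .10 | 1.046 | .0126 | 76.8% |

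**Four-wave check.** Simulated trials used months 0, 3, 6 and 12 with the intercept at 12, 6 schools with 17 per arm in each, complete data and 20,000 runs per case. Assumed within-school structure: 60% random intercept, 40% residual, slope variance .0015(1 − ICC), intercept-slope correlation .3.
- School differences constant over time: R = 1.007, 1.021 and 1.046. Rejection at .017 without school was .0154, .0139 and .0132; with school it was .0160, .0164 and .0178. The Monte Carlo standard error is about .001.
- School effects at baseline and month 12 correlated .5: R = 1.004, 1.014 and 1.030.

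**Can Table 2 change?**
- With the estimate held fixed, t = 1.75 reaches the .017 critical value (2.407 on 200 df) only if 1 − (1.75/2.407)² = .47 of the variance lies between schools.
- The estimate need not stay fixed, because the SAP reports 9% attrition at one year and loss disturbs balance. With 9% random loss in a one-wave simulation (10,000 runs), adding school shifted t with an SD of about .06 to .11 over ICC .02 to .10.
- At ICC .10, t is about 1.75 × 1.046 = 1.83. The gap to 2.407 is 0.577, which is 0.577/.11 = 5.2 SDs.
- At ICC .05, t is about 1.79, with a plausible range of roughly 1.62 to 1.96, so p could fall to about .05 or rise to about .11. For this reason no adjusted p-value is claimed.

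**The case against.** **The consequence is small.** This stands. All 21 contrasts are null at .017, the loss of power is 3 points or less, and the analysis is complete.

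**Silence is not omission.** The SAP is a past-tense summary with results, so the fitted code may have held a school term. A reader might infer that the planned model was abandoned. The documents do not show that: the protocol mentions nesting but does not itself specify a school term. The fair statement is that both documents under-describe the school level.

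**Planned balance is not achieved balance.** Within-school allocation is stated only as a plan, and fuller baseline tables are said to be published elsewhere. Area balance is partial reassurance, since two schools were planned per area, but area is not the stratum. If allocation was in fact not balanced by school, simulated error without school was .0165 to .0176, which is about nominal; only precision is then lost.

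**Schools were probably unequal.** The SAP says most children lived in suburban settings. With assumed school shares of 35/30/12/10/8/5%, the excess in standard error is 0.8%, 2.0% and 4.2% at the three ICCs, so the conclusion holds.

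**Ignored clustering inflates error.** A reader might infer this and apply a cluster design effect. The documents do not support it: families, not schools, are randomised, and arms are compared within schools. Under a common effect the direction is conservative. If effects differ across schools and inference is to schools in general, error can exceed .017. As an illustration, at ICC .05 with an assumed effect SD of .1 or .2 it was .0185 or .0365 without school, and .0208 or .0408 with a school main effect. The documents do not set that target of inference, and a school term would not address it.

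**Conclusion.** The point holds as a minor one. The protocol plans randomisation within school and speaks of nesting in schools; the SAP model describes no school term; and neither document says how school enters.

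The size given (standard errors about 1% to 5% too large, tests slightly conservative, up to 3 points of power lost) rests on four conditions: the model was fitted as described, arms are balanced within school, the effect is common to the schools, and the ICC lies between .02 and .10. The last is an assumption. If school effects drift over time the excess is smaller, about 0.4% to 3.0%.

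A reader might also infer that the reported contrasts are biased, or that the p = .081 trend would strengthen once school is included. Neither follows. Leaving out a randomisation stratum does not bias the contrasts, and with 9% attrition that p-value could move slightly either way.

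**What to change.** Include school in every condition model as a six-level fixed effect. Six schools are few for estimating a variance component, but a random school intercept is acceptable. Report the school-adjusted contrasts beside those in Table 2, with counts of families by school and arm, and state that inference is to these six schools.

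If school was already fitted, correct the SAP's Data Analysis text to say so. In either case, name the unit over which the random intercepts and slopes vary.

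The cost is one classification variable in existing code, about 5 degrees of freedom and no new data; or, if school was already fitted, one sentence of text.
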